5.4 Method of Assigning Subjects to Treatment Groups

Subjects will be randomly allocated in a 1:1 ratio to receive placebo (Arm A) or CMB305 (Arm B) according to a centrally randomized treatment schedule.

An IRT system will use the following stratification factors at the time of randomization:

- Disease status at screening: locally advanced unresectable (LAUR) vs metastatic
- Tumor response during screening: stable disease (SD)/partial response (PR) vs complete response (CR)/no evidence of disease (NED)
- Baseline presence of anti-NY-ESO-1 antibody (yes vs no)

5.5 Blinding

The study subjects, investigators, study site personnel, including the pharmacist, safety laboratory personnel, central imaging readers, sponsor, and representatives of the sponsor involved in the conduct and/or management of the study will be blinded to treatment assignment.

LV305 and its placebo will be identical in appearance; G305 and its placebos will be identical in appearance.

All study treatments (CMB305 or placebo) will be labeled with the study number, a unique number, and any additional information required in accordance with government regulations. Further details will be contained in the Pharmacy Manual provided to study sites.

The blind may be broken in case of a medical emergency when unblinding the treatment is necessary to manage the treatment of a subject. The investigator has the ability to perform unblinding immediately according to emergency unblinding procedures.

5.6 Treatment Modification and Discontinuation

There are no protocol allowed dose reductions or increases.

5.6.1 Treatment Interruptions

If less than a full dose of a study treatment component (LV305 or G305) is administered (eg, less than the four (4) injections of LV305/placebo), document the injections that were administered and the reason the other injections were not administered. The missed injections will not be administered at a later time. Treatment should resume according to the next scheduled dose and visit.

5.6.2 Treatment Delay

Administration of a study treatment component (LV305 or G305) will be delayed for the following adverse reactions:

- A drug-related non-hematological toxicity \geq Grade 2, with the exception of toxicity listed under requirement of permanent discontinuation of study treatment; Grade 2 fatigue alone does not require the withholding of study treatment;
- A drug-related hematological toxicity Grade 4.

Study treatment will resume according to schedule if drug-related toxicity improves to \leq Grade 1 within 4 weeks of onset. If Grade 2 toxicity stabilizes based on the investigator assessment (subject is asymptomatic and controlled), study treatment may resume after consultation with and approval by the Sponsor.

5.6.3 Treatment Discontinuation

Permanent discontinuation of a study treatment component (LV305 or G305) responsible for an adverse event should be considered following discussion with the Sponsor if any of the following drug related adverse events are experienced:

- Severe or life-threatening drug-related adverse events;
- Grade 2 or above drug related adverse events which persist without improvement for >4 weeks. With Investigator and Sponsor agreement, subjects with a drug-related adverse event still at Grade 2 may continue in the study only if asymptomatic and controlled.

For subjects who experience a recurrence of the same \geq Grade 3 drug-related adverse events with rechallenge of study treatment component (LV305 or G305), a consultation between the Sponsor and Investigator will occur to determine whether therapy with study treatment component responsible for the event should be discontinued. A subject who experiences the same drug-related serious adverse events (SAE) of the same Grade or higher with rechallenge, therapy with study treatment component responsible for the event must be discontinued immediately.

5.7 Concomitant Therapy

Except for excluded medications ([Section 5.8](#)), medications for symptoms and supportive management are permitted. During the study, if the use of any concomitant treatment becomes necessary (e.g., for treatment of an AE), the treatment must be recorded on the source document and eCRF, including the reason for treatment, name of the drug, dosage, route, and date of administration. All medications including prescription, over-the-counter (OTC), herbal, and other nutritional vitamins and/or supplements taken within 60 days of Day 1 will be recorded on the eCRF.

5.8 Restrictions

In addition to the restrictions specified in [Section 4.3](#), Exclusion Criteria; subjects must comply with the following restrictions.

5.8.1 Prior Therapy

Subjects cannot have received prior treatment with the following:

- NY-ESO-1-directed immunotherapies

Subjects must have received the last dose of first-line systemic anti-cancer therapy, or the last day of treatment with local regional therapy, if applicable, no more than 28 days prior to Day 1.

The following are prohibited within 21 days prior to the first administration of CMB305 on Day 1 or 5 half-lives of the drug (whichever is sooner):

- Any investigational agent or cancer therapy
- Immunomodulatory agents (including, but not limited to, interleukin-2)

The following are prohibited within 21 days prior to the first administration of CMB305 on Day 1:

- Immunosuppressive medications, including but not limited to, cyclophosphamide, azathioprine, methotrexate, thalidomide, and anti-TNF agents
- Any systemic anti-cancer therapy or local regional therapy (surgical resection, radiotherapy, radiofrequency ablation, cryotherapy)

5.8.2 Prohibited Concomitant Therapy

The following treatments will be prohibited from Day 1 through the end of treatment or until investigator-determined PD (using RECIST v1.1) is documented:

- Any investigational drug other than LV305 or G305 is prohibited prior to documentation of investigator-determined PD (using RECIST v1.1).
- Any chronic treatment with systemic immunosuppressive dose of corticosteroid at supra-physiologic doses within 28 days prior to administration of the first dose on Day 1 through the end of treatment or until investigator-determined PD (using RECIST v1.1) is documented. The use of physiologic doses of corticosteroids may be approved after consultation with the sponsor.
- Other concurrent immunosuppressive medications such as methotrexate, cyclosporine, or azathioprine are prohibited prior to documentation of investigator-determined PD (using RECIST v1.1).
- Concomitant systemic anti-cancer therapy prior to documentation of investigator-determined PD (using RECIST v1.1) is prohibited for symptomatic deterioration or for subjects with NED at time of study entry who develop a new malignant lesion.

- Any systemic anti-cancer therapy or local regional therapy (surgical resection, radiotherapy, radiofrequency ablation, cryotherapy) prior to documentation of investigator-determined PD (using RECIST v1.1), or documented symptomatic deterioration, or for subjects with NED at time of study entry who develop a new malignant lesion.

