3.1.3 Treatment Period

The Treatment period will begin on the day of randomization (Day 1), which is to be within 28 days after the last dose of first-line systemic anti-cancer therapy or last day of local regional therapy, if applicable, and will continue until investigator-determined progressive disease (PD) (using RECIST v1.1), unacceptable toxicity, or 1 year after the first dose, whichever occurs first.

Subjects who meet eligibility criteria will be randomly assigned in a 1:1 ratio to receive one of the following centrally randomized treatments:

- Arm A: Placebo
- Arm B: CMB305

An interactive response technology (IRT) system will use the following stratification factors at the time of randomization:

- Disease status at screening: locally advanced unresectable (LAUR) vs metastatic
- Tumor response during screening: stable disease (SD)/partial response (PR) vs complete response (CR)/no evidence of disease (NED)
- Baseline presence of anti-NY-ESO-1 antibody (yes vs no)

Subjects who are randomly allocated to the placebo arm will not be permitted to cross-over to the CMB305-containing treatment arm at any time before study closure.

Tumor imaging assessments will be performed every 8 weeks after Day 1 and radiographic evidence of disease progression will be determined by the investigator using RECIST v1.1. Subjects with a global deterioration of health status requiring discontinuation of study treatment but without objective evidence of disease progression (symptomatic deterioration) will be considered as having PD for the purpose of determining PFS. Radiographic images (e.g., computed tomography [CT] scan or magnetic resonance imaging [MRI]) will also be submitted to an IRC for storage and will be available for evaluation by a central reader, if requested by the sponsor. Details for the collection and evaluation of radiographic images are included in the Radiology Manual provided to the study sites.

Tumor biopsy samples for NY-ESO-1 expression will be obtained from all subjects during the Pre-screening period as described in [Section 3.1.1](#) (either archival tumor tissue or a fresh biopsy sample). All subjects will provide peripheral blood samples for anti-NY-ESO-1 antibody assay at the screening visit for stratification.

Quality of life will be assessed up to 12 months from Day 1.

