Safety will be monitored by evaluating the frequency and severity of adverse events (AEs), serious adverse events (SAEs), clinical laboratory abnormalities, immunogenicity and persistence of LV305. Local laboratory test values will be used for treatment decisions and subject care; central laboratory test values will be used in the analysis of safety.

In addition, at only select US sites, the following will be collected:

Peripheral blood samples for the anti-NY-ESO-1 T cell and antibody assays will be obtained prior to start of study treatment from subjects on Day 1, Day 92, and Day 365 for subjects who have not had a progression event. A tumor biopsy will be obtained at screening, Day 92, and Day 365 for subjects who have not had a progression event. An additional tumor biopsy at time of progression event will be encouraged.

3.1.4 Post-treatment Period (For Subjects Who Discontinue Study Treatment for Reasons Other Than Disease Progression)

The Post-treatment period will begin at the end of treatment and will continue until investigator-determined radiographic PD (using RECIST v1.1) is documented.

Subjects will continue to undergo imaging until the time of disease progression. At the time of disease progression, subjects will enter the Long-term Follow-up period.

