6.3.1.3 Imaging During Treatment to the Time of Disease Progression

Tumor imaging assessments will be performed and evaluated every 8 weeks after Day 1 until investigator-determined PD (using RECIST v1.1) is documented. Disease progression will be assessed by the investigator using RECIST v1.1. For each subject, the images obtained during the Treatment period must have been collected using the same imaging method for all images during the Pre-screening and Screening periods. Subjects who have a global deterioration of health status that is attributed to progressive disease and leads to discontinuation of study treatment, but who are unable to provide radiographic evidence of disease progression (symptomatic deterioration), will be considered as having PD at the time of documented global deterioration of health for the purpose of determining PFS. Radiographic images (e.g., CT scan or MRI) will also be submitted to an IRC for storage and will be available for evaluation by a central reader, if requested by the sponsor. Details for the collection and evaluation of radiographic images are included in the Radiology Manual.

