6.5.2 Removal from Study Drug

While subjects will be encouraged to continue participation in the study for safety and survival follow-up, subjects **MUST** be discontinued from receiving further study drug for the following reason:

- Progressive disease by RECIST v1.1 criteria
- Withdrawal of informed consent from study treatment
 - Subject will continue to be followed for imaging and quality-of-life assessment
- Any clinical AE that meets treatment discontinuation criteria in section 5.6 or any other reason that, in the opinion of the investigator, indicates that continued dosing on the study is not in the best interest of the subject
 - Subject will continue to be followed for imaging and quality-of-life assessment

Subjects will be permitted to continue study drug if the RECIST v1.1 criteria for PD are met provided they meet all the following criteria:

- Evidence of clinical benefit as assessed by the investigator
- Absence of symptoms and signs (including worsening of laboratory values) indicating unequivocal progression of disease
- No decline in ECOG performance status that can be attributed to disease progression
- Absence of tumor growth at critical anatomical sites (e.g., leptomeningeal disease) that cannot be managed by protocol-allowed medical interventions
- Subjects for whom approved therapies exist must provide written consent to acknowledge deferring these treatment options in favor of continuing study treatment at the time of initial apparent progression. Study treatment will be discontinued upon commencement of subsequent systemic anti-tumor therapy.

No unblinding will be permitted for subjects who continue study treatment beyond progression.

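### Protocol Section 5.8.2, read literally, both bans and allows systemic anti-cancer therapy after documented symptomatic deterioration; most likely a drafting error in its fourth bullet

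*Protocol*

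**What the plan says.** Protocol Section 5.8.2 opens with a lead-in under which the listed treatments are "prohibited from Day 1 through the end of treatment or until investigator-determined PD" (RECIST v1.1) is documented. Two of its five bullets deal with anti-cancer therapy.

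- Fourth bullet: "Concomitant systemic anti-cancer therapy prior to documentation of investigator-determined PD (using RECIST v1.1) is prohibited for symptomatic deterioration". It adds subjects with no evidence of disease (NED) at entry who develop a new malignant lesion.
- Fifth bullet: any systemic or local regional therapy is barred "prior to documentation of investigator-determined PD (using RECIST v1.1), or documented symptomatic deterioration", followed by a similar NED clause.

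Section 3.1.3 describes symptomatic deterioration as a global decline in health that requires stopping study drug. Subjects in that state "without objective evidence of disease progression (symptomatic deterioration) will be considered as having PD for the purpose of determining PFS". Section 6.3.1.3 says that they "will be considered as having PD at the time of documented global deterioration of health for the purpose of determining PFS".

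**The concern.** Sites use Section 5.8.2 to decide when a subject may move on to other therapy. Where two bullets end the same ban at different points, the stricter one may be followed. The subject at risk is getting worse, has stopped study drug and has no measured RECIST progression. Section 8.18 makes a cautious reading more likely: it forbids deviations without sponsor agreement and ethics committee approval, allows exceptions only for medical emergencies, and rules out waivers. What is at stake is access to next-line treatment. Sites reading the bullets differently could also record the same conduct as a deviation or not. The efficacy evaluable set excludes major violations, but neither document says whether this would count as one.

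**Working it through.** The plan gives no figure to reproduce on this point. The check compares the texts and then reads the scan schedule.

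**1. One case under each rule.** Take a subject with symptomatic deterioration documented by the investigator and no RECIST progression.

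| Rule | End of ban on systemic therapy | Answer for this subject |
|---|---|---|
| Fourth bullet, literal | RECIST progression documented | Still prohibited |
| Fifth bullet | RECIST progression or documented deterioration | No longer prohibited |

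The subject and the therapy are the same, and the answers are opposite.

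**2. Can the case arise?** Yes. Section 3.1.3 defines the condition by the absence of objective progression, and Section 6.3.1.3 by the inability to provide radiographic evidence of it.

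**3. Could RECIST progression be documented later?** Possibly. Section 3.1.4 says "Subjects will continue to undergo imaging until the time of disease progression". Section 6.5.2 says of subjects taken off study drug at the investigator's judgement: "Subject will continue to be followed for imaging and quality-of-life assessment". Section 7.7.1 ends image collection when a new line of treatment begins. A site following the fourth bullet would therefore keep looking for RECIST progression while the subject stays without systemic therapy.

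**4. Scheduled interval to the next scan.** Section 6.3.1.3 says "Tumor imaging assessments will be performed and evaluated every 8 weeks after Day 1 until investigator-determined PD (using RECIST v1.1) is documented". Table 2 footnote l gives the same 8-week interval for up to 1 year. Footnote c changes it to 12 weeks ±7 days once a subject reaches 12 months on study without progression. If a site relied on scheduled scans alone, the wait for the next one would be up to 8 weeks before month 12 and up to 12 weeks (±7 days) after it. An unscheduled scan would shorten the wait. A scan that did not show RECIST progression would lengthen it.

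**5. Primary PFS.** Section 7.7.1 lists symptomatic deterioration as a PFS event and uses whichever event occurs first. SAP Section 5.1.1.1 lists it among investigator-determined progression events. The event is fixed on the deterioration date, so therapy started afterwards neither moves nor censors it under either bullet.

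**6. Alpha and power.** The one-sided 0.0125 per primary endpoint and the targets of 141 PFS events and 179 deaths do not depend on Section 5.8.2.

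**7. Time to next treatment (TTNT).** SAP Section 5.1.2.1 counts to the start of the next intervention, so a delayed start would lengthen it for that subject. The documents give neither the share of subjects who deteriorate symptomatically nor any delay, so no effect can be computed.

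**The case against.** The strongest reply is that the conflict disappears in context. The section concerns concomitant therapy, and the lead-in stops the bans at the end of treatment. Deterioration as defined requires stopping study drug, so later therapy is not concomitant with it. Appendix 1 records deterioration as a progression event on the investigator's date, without limiting that to PFS, and SAP Section 5.1.1.1 agrees. On that view, documenting deterioration also meets the fourth bullet's end point. The fourth bullet might also be read as covering only deterioration not yet documented.

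Much of this stands: it shows which rule was meant and makes harm unlikely. It does not remove the conflict, for four reasons.

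- The lead-in joins two end points with "or" and does not say that the earlier one applies; the fourth bullet then sets its own, RECIST progression.
- If concomitant means only while on study drug, the fourth bullet's reference to deterioration has almost nothing to act on.
- Sections 3.1.3 and 6.3.1.3 attach the progression label for determining PFS, and the fifth bullet names deterioration separately from RECIST progression.
- The SAP list is an analysis definition, not a treatment rule for sites.

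A reader might also infer more than the documents support.

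- *The ban is permanent for these subjects.* It is not, because imaging continues and RECIST progression may be documented later.
- *The wait is about 13 weeks, from the three-monthly post-treatment header in Table 2.* That is a visit header. Section 6.3.1.3 and footnotes c and l set the imaging intervals given above.
- *The primary PFS result is distorted.* It is not, because deterioration is itself the event.

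**Conclusion.** The two bullets conflict on a literal reading, and the rest of the text points to the fifth as the intended rule. This is most likely a drafting error in an operative treatment rule, not a design decision to withhold therapy. The possible harm is to patient care: delayed next-line treatment in a subject who gains nothing further from the restriction. It depends on a site following the fourth bullet against the surrounding text, and nothing in the documents shows that any site would. The scan intervals describe how such a wait would be paced; they do not estimate a delay that will occur. The correction is worth making but low in priority.

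**What to change.** Delete the fourth bullet of Section 5.8.2 or align it with the fifth. Systemic and local regional anti-cancer therapy would then be prohibited only until the first of:

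- investigator-determined RECIST v1.1 progression, including a new malignant lesion in a subject with NED at entry (consistent with Appendix 1, Table 8); or
- documented symptomatic deterioration.

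This wording also tidies the NED clauses. The cost is one sentence in the next amendment and a short memo to sites. It needs no extra procedures, subjects or analyses.

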5.9 Treatment Compliance

All doses of study drug will be administered under the supervision of the investigator or identified sub-investigator(s). Appropriate study personnel will maintain records of study drug receipt and dispensing. Any discrepancy regarding the dose administered and the reason for the discrepancy will be recorded in the eCRF.

5.10 Packaging and Labeling

CMB305 and its matching placebos will be manufactured, packaged, and labeled according to Good Manufacturing Practices (GMP) and Good Clinical Practices (GCP).

5.11 Storage and Accountability

Full details on the storage of CMB305 and matching placebo will be provided in the Pharmacy Manual and on the investigational product label.

LV305 drug product is stored at -90°C to -60°C. For G305, the NY-ESO-1 protein is stored at -90°C to -60°C and GLA-SE is stored at 2°C to 8°C.

Under no circumstances is it permitted to use study supplies for any purposes other than those specified in this protocol.

The investigator or a medically qualified, authorized delegate will be provided with forms to enable accurate recording of all study doses at the study site at all times. The investigator, or designee, must sign a statement that he/she has received study drug supplies intended for the study. At any given time, the amount of study drug supplied, used, and unused at the study site must match. An accounting must be given of any discrepancies.

6.0 STUDY PROCEDURES

All study procedures detailed in Sections 6.1 to 6.3 will be performed at the time points stipulated in the schedule of events for the Pre-Screening and Screening periods (Table 1) and for the Treatment through Long-term Follow-up periods (Table 2).

6.1 Informed Consent or Assent

All subjects and legal authorized representatives must provide written informed consent (if ≥ 18 years of age) or assent (if 12 to < 18 years of age) at Pre-screening and Screening. Two informed consents/assents will be used.

The Pre-screening ICF/assent form will allow for IHC testing of the tumor sample (fresh or archival) for the presence of NY-ESO-1, and review of the tumor images (CT or MRI) collected before and after administration of the first dose of first-line systemic anti-cancer therapy.

The Main Study ICF/assent allows for participation in the study and must be signed before initiation of any Screening study-related procedures. Before the Main Study ICF/assent can be signed, results of IHC testing for the presence of NY-ESO-1 ($\geq 1\%$ expression) must be available from the central laboratory, and the investigator-evaluated tumor response (SD or better using RECIST v1.1) to first-line systemic anti-cancer therapy must be documented.

Prior to any involvement in study-related activities, an institutional review board (IRB)/independent ethics committee (IEC)-approved written ICF/assent must be signed and dated by the subject and/or by the subject's legally acceptable representative according to local regulations. Documentation of local regulations regarding what constitutes legally acceptable representation should be filed at the study site. A copy of the signed and dated ICF and any other required forms to meet local or country-specific regulations must be given to the subject and the legally acceptable representative. During the consent process, the person obtaining consent must inform the subject of all elements of the study. No protocol-specific procedures, including screening procedures, are to be performed until the subject has signed and dated an IRB/IEC-approved ICF/assent. The study begins with the signing and dating of the Main Study ICF/assent form.

